Cerebral infarction is the main type of stroke which has become hotspot and difficulty of the research in medical science because of its high morbidity, disability and mortality. Stroke has caused great harm and burden to patients' family and society. It was reported by WHO that 80% of stroke patients have different degrees of limb dysfunction. With the intervention of rehabilitation therapy, some patients would recover in different degrees within 6 months. However, more than 60% of patients still remain upper limb dysfunction in chronic phase. According to the literature, only 15% of patients with stroke can recover to 50% of the original hand function. Only 3% of them can recover to more than 70% of the original. Because the motor function recovery of upper limb and hand is more difficult than that of lower limb. So we often pay more attention to the motor function recovery of lower limb and ignore the motor function rebuilding of upper limb. In addition, the disuse of affected hand and compensatory of unaffected hand of stroke patients lead to "learning without practice" and hand muscles contracture. If we start rehabilitation training now, the effects of rehabilitation training will be unpleasant and reduce the activities of daily living and quality of life seriously. [name], the famous abdominal acupuncture expert, using abdominal acupuncture treated hemiplegic patients with stroke and achieved remarkable effects. The acupuncture points of abdominal acupuncture form a turtle chart at the abdomen. Zhongwan point is on behalf of head, Shangqu point is on behalf of neck and shoulder joint, Wailing point, Upper rheumatic point and Upper rheumatic external point are on behalf of shoulder in the turtle figure. The affected upper limb motor function can be improved by acupuncturing the Zhongwan, Shang Qu, Wailing, Upper rheumatic and Upper rheumatic external points. Because it can regulate and control the head, shoulder and hemiplegic limb and achieve the "holographic feedback" phenomenon. But the exact mechanism is not yet clear. Therefore, it is very important and urgent to use modern medical technology to elucidate its treatment mechanism.

3. Purpose

3.1 Hemiplegic patients with first onset stroke were treated with abdominal acupuncture combined with upper limb rehabilitation training to observe the recovery of upper limb motor function, the muscles synergy monitored by sEMG, local brain area activation by fMRI and the integrity of pyramidal tract of cerebral white matter.

3.2 To analyze the changes of upper limb motor function the relationship between the changes and sEMG or brain fMRI

3.3 to explore the possible mechanism of abdominal acupuncture combined with upper limb rehabilitation training on brain plasticity of upper limb motor function recovery in hemiplegic patients with stroke.

4. Reporting Units and Research Units

Reporting unit: Rehabilitation Department of Guangdong Provincial Hospital of Chinese Medicine

Address: [name]

Research Director: [name] e-mail:[contact]

Clinical Auditor: [name] e-mail:[contact]

Head of Clinical Research Unit: Rehabilitation Department of Guangdong Provincial Hospital of Chinese Medicine

Address: [name]

Research Director: [name] e-mail:[contact]

Participating Units:

Rehabilitation Department of Guangdong Provincial Hospital of Chinese Medicine

Director: [name]

Chinese University of Hong Kong

Director: [name]

5. Research Design

5.1 Case selection: 66 patients diagnosed with initial stroke by CT/MRI and hospitalized in rehabilitation department of our hospital who meet the inclusion criteria will be included.

5.2 Random method: Patients met the inclusion criteria will be randomized into 3 groups by MATLAB stratified randomization software:

Treatment group A: abdominal acupuncture +upper limb rehabilitation training, 22 cases;

Treatment group B: Sham abdominal acupuncture +upper limb rehabilitation training, 22 cases;

Control group : upper limb rehabilitation training only , 22 cases.

Sample size calculation: Using the SAMPSIZEPWR function calculation of MATLAB software Statistic Toolbox (Statistics Toolbox) to calculate, it is assumed that Fugl-meyer assessment (FMA) is the outcome index, and the FMA before rehabilitation training is also assumed to be 30 ± 10 (average \pm Standard deviation), the FMA after rehabilitation training is 37 (average). The amount of effect between groups is ~ 0.7 . If 0.8 of the statistical verification force is required, the sample size is 19 cases calculated by T-Test. Taking some uncontrollable factors that may causing dropping off into consideration, each group increases 3 cases with a 15% fall rate. Each group will include 22 cases.

5.3 Inclusion Criteria:

- ① First onset stroke, Left hemiplegia, Right-handed, and diagnosed by brain CT or MRI;
- ② Age 35 to 75 years old;
- ③ Course of disease 0.5 to 3 months with stable vital signs;
- ④ No cognitive impairment. Can understand and execute commands. MMSE score more than 7 points. ;
- ⑤ Can control the sitting balance. Brunnstrom stage of hemiplegic upper limb and hand is IV or V , Fugl-Meyer Motor Assessment score of upper limb 20-50 point;
- ⑥ Agree to sign the informed consent;
- ⑦ Unilateral neglect.

5.4 Exclusion Criteria:

- ① Recurrent stroke, subarachnoid hemorrhage, brain tumors patients;
- ② Contraindication to undergo a 3T MR imaging;
- ③ Claustrophobia;
- ④ Have severe heart, hepatic or renal failure;
- ⑤ Don' t cooperate with the treatment;
- ⑥ Have participated in other clinical trails recently.

5.5 Treatment Method:

Treatment group A: abdominal acupuncture +upper limb rehabilitation training;

Treatment group B: Sham abdominal acupuncture +upper limb rehabilitation training;

Control group : upper limb rehabilitation training only .

All the treatments above last for 30mins a time, once a day, five times a week, totally 4 weeks.

Upper limb Rehabilitation Training programme is based on the recommendations of the American AHA-ASA-2016-Stroke Rehabilitation Guideline , including instrumental activities of daily life training and upper limb operation therapy.

A: Instrumental activities of daily life training:

Extend elbow (side): Subject attempts to reach across the table by extending the elbow (to the side).Extend elbow (to the side), with weight: Subject attempts to push the sandbag against outer wrist joint across the table by extending the elbow.Extend elbow (to the side), with weight: Subject attempts to push the sandbag against outer wrist joint across the table by extending the elbow. Hand to box (front): Subject attempts to place hand on the box.Pick up paper clip (front): Subject attempts to pick up paper clip by using a pincer grasp.Stack 3 checkers and flip 3 cards.Turning the key in the lock,fold towel,pick up the basket by grasping the handle and place it on the beside

table. Treatment Duration: 45 minutes a session, once a day, 5 times a week for 4 weeks.

B: Upper limb operation therapy:

According to the patient's specific situation, take the routine operation treatment. It includes the training of shoulder blades loosening, the active assistant and active training of the side upper limb, the joint activity training of the upper limb, the upper extremity training, and the grasping and opening of the side finger. Mainly with the side training, but also included a small number of contralateral auxiliary side training. Treatment time: 30 minutes/times, 1 times/day, 5 days/week, total 4 weeks.

5.6 Evaluation Method:

(1) Screening Assessment

Simple intelligent mental state scale (MMSE), and Brunnstrom upper limb movement staging will be evaluated once when included.

(2) Primary Outcome Measure:

Functional magnetic resonance imaging (fMRI) and surface electromyography (sEMG) are the two primary outcome, which will be tested before and 4 weeks after treatment, twice totally.

(3) Secondary Outcome Measure:

Wolf Motor Function Test; Brunnstrom staging of upper limb movement; Fugl-Meyer Motor Assessment of upper limb; Modified Barthel Index.

Time Frame: Before treatment, 2 weeks and 4 weeks after treatment, 3 times totally.

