Using fMRI and sEMG to Evaluate the Effects and Mechanism on Abdominal Acupuncture Combined With Upper Limb Rehabilitation Training on Brain Plasticity of Hemiplegic Patients With Stroke

Head of Clinical Research Unit: Guangdong Provincial Hospital of Chinese Medicine

Director of Clinical Research: [name]

Clinical Research Participating Unit: Guangdong Provincial Hospital of Chinese Medicine, Chinese University of Hong Kong.

Reporting Unit: Guangdong Provincial Hospital of Chinese Medicine

Research Director: [name]

Statistical Analysis Plan

Statistical analysis of our research will use SPSS 18.0 and MATLAB statistical software. The measurement data adopt T-Test, counting data use repeated measurement variance analysis and X2 test. And the image analysis adopt SPM8 software.

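### Randomisation is stratified, but the SAP's t-test and chi-square test have no stratum term; if the strata are prognostic and balanced, this costs precision and power.

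*Protocol*

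**What the plan says.** Protocol section 5.2 (Random method) states: "Patients met the inclusion criteria will be randomized into 3 groups by MATLAB stratified randomization software". The three arms are to have 22 patients each. Neither document gives the stratification factors, the number of strata or the block size.

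The SAP's rule for scalar and categorical data is one sentence: "The measurement data adopt T-Test, counting data use repeated measurement variance analysis and X2 test". On imaging it says only "And the image analysis adopt SPM8 software". No stratum factor, covariate or stratified test is named. The terms of the repeated-measures model and the SPM8 design matrix are not given.

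The sample size paragraph in 5.2 supplies the effect used below: "The amount of effect between groups is ~ 0.7", with 0.8 power, 19 per group, and 3 added per group for 15% dropout. No significance level is stated.

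**The concern.** Stratified allocation is normally used to make the arms alike on factors expected to influence outcome. When it succeeds, differences between strata no longer contribute to the chance difference between arms, so the true variance of the arm comparison falls. A two-sample t-test does not know this. It estimates the standard error from the total spread within each arm, which still contains the between-stratum part. A plain chi-square test does the same with the pooled proportion. Both then report more uncertainty than the design has.

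What is at stake is efficiency. The precision bought by stratifying would not reach the reported intervals and p-values, in a trial with only 22 patients per arm.

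**Working it through.** **Inputs from the documents.** 22 per arm; standardised effect 0.7 (from 30 to 37 on the FMA, SD 10: 7/10); 15% dropout; power 0.8.

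**Assumptions.** Two-sided 5%. One pairwise comparison of 22 v 22. A two-level stratum split 11/11 in each arm. R² is the share of outcome variance that the stratum explains; the documents give nothing to fix it, so it is varied from 0 to 0.3.

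**Step 1: the plan's own figure.** A two-sided 5% one-sample t-test at effect 0.7 has power 0.799 with n = 18 and 0.823 with n = 19, which reproduces the stated 19. One-sided 5% would give 15, which supports the two-sided assumption. For dropout, 19 × 1.15 = 21.85, rounded to 22. A two-sample t-test at effect 0.7 with 22 per arm has power 0.62. That gap is a separate matter, but 0.62 is the starting point for the power comparison below.

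**Step 2: t-test under exact balance.** With total variance 1, the t-test estimates the variance of the arm difference as about 2/n, while its true value is 2(1 − R²)/n. So:

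- estimated SE / true SE ≈ 1/√(1 − R²)
- true type I error ≈ 2[1 − Φ(1.96/√(1 − R²))]

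For R² = 0.3: √0.7 = 0.837, 1.96/0.837 = 2.343, giving 1.9%. Simulation (40,000 runs per row) agrees with the formula:

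| R² | SE ratio, formula | Type I, formula | Type I, simulated t-test | Power at 0.7: t-test | Power at 0.7: with stratum term |
|---|---|---|---|---|---|
| 0 | 1.00 | 5.0% | 4.9% | 62% | 62% |
| 0.05 | 1.03 | 4.4% | 4.3% | 63% | 64% |
| 0.10 | 1.05 | 3.9% | 3.8% | 63% | 67% |
| 0.20 | 1.12 | 2.8% | 2.8% | 63% | 72% |
| 0.30 | 1.20 | 1.9% | 1.9% | 63% | 77% |

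With the stratum in a linear model, simulated type I error stayed at about 5% in every row.

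**Step 3: chi-square test.** Same layout, 200,000 runs. With event rates in the two strata of 0.5/0.5, 0.4/0.6, 0.3/0.7 and 0.2/0.8, the unadjusted test rejected a true null in 4.9%, 4.5%, 3.2% and 1.4% of runs.

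**Step 4: dropout.** Random loss of 15% undoes part of the balance. About 0.15 of the between-stratum variance returns to each arm mean, so the true variance factor becomes 1 − R² + 0.15R² = 1 − 0.85R².

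- R² = 0.2: 1.96/√0.83 = 2.15, type I error 3.1%.
- R² = 0.3: 1.96/√0.745 = 2.27, type I error 2.3%.

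A simulation with three arms, blocks of 6 within 2 to 8 strata (assumed) and 15% dropout, where incomplete blocks loosen the balance further, gave 4.6–4.7%, 3.8–4.1%, 3.3–3.4% and 2.4–2.8% at R² = 0.05, 0.1, 0.2 and 0.3. Intervals were then about 1%, 4%, 7–9% and 11–14% too wide. A fair single figure at R² = 0.3 is about 2.6%. The power columns in Step 2 assume no dropout.

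**Step 5: when the effect vanishes.** If allocation within strata is unrestricted, so that balance is not enforced, the unadjusted t-test simulated at 4.8% to 5.1%. If the stratum does not predict outcome (R² = 0), it is also at about 5%.

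**The case against.** The strongest reply is that nothing in the documents shows the effect will occur. It needs strata that predict outcome and allocation balanced within them, and neither is documented. A reader might infer that the planned tests definitely run below 5%, or that the p-values are wrong whatever strata the software used. Step 5 shows that neither follows. The plan also states no alpha, standard error or interval, so no printed figure is in error.

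The higher R² values may be optimistic too. Section 5.3 already restricts entry to first stroke, left hemiplegia, right-handed patients, Brunnstrom stage IV or V and FMA 20 to 50, which leaves less for strata to explain. If change scores are tested, and the SAP does not say, the strata may explain less again.

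A reader might also extend the point to the primary outcomes as a whole. The protocol names fMRI and sEMG as primary. The SPM8 model's terms are unstated, as are those of the repeated-measures analysis, so a missing stratum term is not shown in either. The computed figures apply to a scalar t-test and to chi-square only.

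These points stand, and they limit the claim to a conditional one of unknown size. They do not remove it. Balance on prognostic factors is the usual reason to stratify, the SAP names two tests that ignore it, and the remedy costs almost nothing if the strata prove uninformative.

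**Conclusion.** The point holds in conditional form. The allocation is stratified, and the SAP's t-test and chi-square test take no account of it. If the strata are prognostic and balanced, reported intervals will be too wide and the tests conservative. There is no inflation of false positives, and a reader should not take this as a threat to the validity of a positive result; the loss is in precision and power.

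For an assumed R² of 0 to 0.3 with two balanced strata of 22 v 22, type I error falls from about 5.0% to 1.9% (about 2.6% at R² = 0.3 after dropout). The power forgone at effect 0.7 is 0 to about 13 or 14 points. The true size cannot be worked out until the factors are named. This is an inexpensive improvement that should be made. It is secondary to the gap between the sample size basis and a two-arm comparison.

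**What to change.** - In section 5.2, list the factors and levels that the MATLAB routine stratifies on, and say how balance within strata is enforced.
- In the SAP, replace "The measurement data adopt T-Test" with a linear model of arm plus those factors for between-arm comparisons of scalar outcomes (sEMG measures, FMA, Wolf, Barthel).
- Replace the plain chi-square test with a Cochran-Mantel-Haenszel test stratified by the same factors.
- State the terms of the repeated-measures model and the SPM8 second-level model, and include the same factors as regressors.
- State the significance level and sidedness.

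The cost is SAP wording and one degree of freedom per non-reference level of each factor (more if factors are crossed, so the strata should be few with 22 per arm). No extra patients or data are needed, since the stratum must be known at randomisation. If the strata turn out not to be prognostic, the terms change almost nothing: at R² = 0 the simulated power was 62% with or without them.

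### The 19 per group matches a one-sample before-after t-test, not the between-group comparison claimed; on the plan's own inputs, power between two arms is about 0.56, not 0.8

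*Protocol*

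**What the plan says.** The calculation is the paragraph on sample size in Protocol section 5.2. It names the software ("Using the SAMPSIZEPWR function calculation of MATLAB software Statistic Toolbox (Statistics Toolbox) to calculate") but not whether the one-sample or two-sample option was chosen, and it gives neither alpha nor the number of sides.

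- Outcome used for sizing: "it is assumed that Fugl-meyer assessment (FMA) is the outcome index".
- Starting value: "the FMA before rehabilitation training is also assumed to be 30 ± 10".
- Value under the alternative: "the FMA after rehabilitation training is 37 (average").
- Effect: "The amount of effect between groups is ~ 0.7".
- Result: "If 0.8 of the statistical verification force is required, the sample size is 19 cases calculated by T-Test".
- Dropout: "each group increases 3 cases with a 15% fall rate", giving 22 in each of three arms.

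The same section lists the arms. All three receive upper limb rehabilitation training, and the third receives nothing else: "Control group : upper limb rehabilitation training only , 22 cases". The SAP specifies a t-test for measurement data. It names no baseline-adjusted model and does not say whether final scores or changes are compared.

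**The concern.** The effect of 0.7 is (37 − 30)/10, the standardised gain from before to after training. A gain of that kind is expected in every arm, because every arm trains. The question the randomisation answers is how much more one arm gains than another, and no figure for that appears in either document. Relabelling the within-arm gain as a between-group effect mixes two quantities. It also appears to have led to a sample size formula for one group rather than two.

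This is the only power statement in the plan; no calculation is given for the fMRI or sEMG outcomes. A reader who trusts the 0.8 would give a non-significant comparison between arms more weight as evidence against an acupuncture effect than it deserves.

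**Working it through.** **Inputs.** From Protocol section 5.2: means 30 and 37, SD 10, so d = 7/10 = 0.7; target power 0.8; 19 per group before dropout and 22 after; dropout 15%. Assumed, because not stated: two-sided alpha 0.05, and SD 10 in both arms. Power is exact, from the noncentral t distribution.

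**1. Reproducing the plan's 19.** One-sample t-test: df = n − 1, noncentrality = d√n.

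- n = 18: 0.7 × √18 = 2.970, critical t = 2.110, power 0.799.
- n = 19: 0.7 × √19 = 3.051, critical t = 2.101, power 0.823.

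The smallest n reaching 0.8 is 19, an exact match.

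**2. The comparison the trial makes.** Two-sample t-test, n per arm: df = 2n − 2, noncentrality = d√(n/2).

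| n per arm | Noncentrality | Critical t | Power |
|---|---|---|---|
| 19 | 0.7 × √9.5 = 2.158 | 2.028 | 0.556 |
| 22 | 0.7 × √11 = 2.322 | 2.018 | 0.621 |
| 33 | 0.7 × √16.5 = 2.843 | 1.998 | 0.7997 |
| 34 | 0.7 × √17 = 2.886 | 1.997 | 0.812 |

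So 34 evaluable per arm are needed, or 34/0.85 = 40 per arm after 15% dropout.

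**3. Would another convention give 19?** A one-sided two-sample test at 0.05 needs 26 per arm, with power 0.681 at 19 and 0.739 at 22. Two arms of 19 reach 0.8 only at one-sided alpha 0.10 (equivalently two-sided 0.20), which neither document mentions.

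**4. What the planned size can detect.** Solving for d at 80% power, two-sided 0.05:

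- 19 per arm: d = 0.934, or 0.934 × 10 = 9.3 FMA points.
- 22 per arm: d = 0.865, or 8.6 points.

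**5. If the difference between arms is smaller than the gain within an arm.** The documents give no value. For illustration only, true differences of 3.5 and 5 points (d = 0.35 and 0.5) give power 0.18 and 0.32 with 19 per arm.

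**6. Rounding of the effect.** The plan gives d as approximate. For d from 0.65 to 0.75, two-sample power at 19 per arm runs from 0.496 to 0.614.

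**7. Dropout.** 22 × 0.85 = 18.7, just short of 19. The allowance should be 19/0.85 = 22.35, so 23. Three in 22 covers 13.6%. The plan's 22 follows from 19 × 1.15 = 21.85 rounded up, which applies the percentage to the wrong base. The gap is one patient per arm.

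**The case against.** Several points can be made for the plan.

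- **The one-sample origin is inferred.** This is true, since the software option is not named. The inference is strong: the inputs are a before mean with SD and an after mean, and 19 comes out exactly. The main conclusion does not need it, because no unadjusted two-sample t-test at alpha 0.05, one- or two-sided, reaches 0.8 with 19 or 22 per arm at d = 0.7.
- **Using the baseline could recover power.** This is the strongest objection. FMA is measured before treatment, and the SAP does not exclude a t-test on change scores. With 19 per arm and an assumed baseline to week-4 correlation of 0.5, 0.6, 0.7 or 0.8, a t-test on change has power 0.56, 0.65, 0.77 or 0.91. Baseline-adjusted ANCOVA gives 0.68, 0.75, 0.84 or 0.94. But neither document states a correlation, names ANCOVA or says that change is the variable tested, so the plan cannot claim this gain as written.
- **FMA is secondary and the aims are partly exploratory.** Protocol section 5.6 does make fMRI and sEMG the primary outcomes, and no decision rule rests on FMA. Even so, the trial's size is justified by this calculation alone, and it claims 0.8 without qualification.
- **The 0.56 accepts 7 points as a between-arm difference.** That is correct. It shows what the plan's own inputs deliver and does not estimate power for the real contrast, which is unspecified. It also ignores multiplicity: splitting 0.05 over three pairwise comparisons would give 0.37 with 19 per arm and 0.44 with 22.
- **The dropout slip is small.** Agreed; it is secondary.

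**Conclusion.** The concern holds. The stated 19 for 0.8 power does not follow for a comparison between arms. Taking 0.7 at face value, power is 0.56 with 19 evaluable per arm and 0.62 with all 22; 80% power needs 34 per arm. These figures rest on two-sided alpha 0.05 (assumed), SD 10 in both arms, an unadjusted t-test and no multiplicity correction. One-sided testing raises them to 0.68 and 0.74, still below 0.8. The effect itself is mislabelled, whichever of these assumptions is used: it is a within-arm gain, and the plan gives no difference between arms. The paragraph must be corrected.

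**What to change.** Keep 66 patients and rewrite the sample size paragraph in Protocol section 5.2 along these lines:

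> With 22 patients per group (about 19 evaluable), a two-sided two-sample t-test at alpha 0.05 has 56% power (62% without dropout) for a 7-point between-group difference in FMA with SD 10. Power of 80% applies to a difference of about 9.3 points (8.6 without dropout).

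With it:

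- Remove the statement that the before-after 0.7 is a between-group effect. Present the 7 points as a reference difference, or replace it with a justified difference between arms.
- State alpha, the number of sides, and which pairwise comparison the figure refers to.
- Correct the dropout allowance: either say that 22 retains 19 at up to 13.6% loss, or that 15% loss leaves 18.7 on average.

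Optionally, the power claim can rest on baseline-adjusted ANCOVA, which must then also be written into the SAP. With 19 per group it reaches 80% for 7 points only if the baseline to week-4 correlation is about 0.66 or higher, so that value would need support.

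The cost is one reworded paragraph, plus one sentence in the SAP if ANCOVA is adopted. No patients, visits or procedures are added; the stated power becomes less favourable.

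### Drop-off is met only by 3 extra patients per group; the named tests would by default use only patients with a week-4 value, which can bias the arm contrast if leaving depends on early progress and differs by arm

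*Protocol*

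**What the plan says.** The sample size paragraph in Protocol 5.2 starts from FMA: "the FMA before rehabilitation training is also assumed to be 30 ± 10", a mean of 37 afterwards, and "The amount of effect between groups is ~ 0.7". It concludes that "the sample size is 19 cases calculated by T-Test" and adds the allowance: "each group increases 3 cases with a 15% fall rate. Each group will include 22 cases". This is the only provision for patients who leave.

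Protocol 5.6 measures the two primary outcomes, fMRI and sEMG, twice: before treatment and at 4 weeks. The secondary outcomes (Wolf, Brunnstrom, FMA, Modified Barthel) have an intermediate visit: "Time Frame: Before treatment, 2 weeks and 4 weeks after treatment, 3 times totally".

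The SAP names the tests in one sentence: "The measurement data adopt T-Test, counting data use repeated measurement variance analysis and X2 test". It adds only the software. It gives no analysis set, no handling of missing values and no sensitivity analysis.

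**The concern.** Spare enrolment replaces numbers. It does not restore comparability if the patients who leave differ from those who stay. A t-test on week-4 values, or on change to week 4, cannot use a patient without week 4. Classical repeated-measures ANOVA drops a patient with any visit missing. With no other rule written, the named tests reduce to a complete-case comparison at week 4.

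This design gives some reason to guard against that. Treatment runs five days a week for four weeks, and the control arm receives no needling, real or sham, so its patients can know their allocation. Reasons for leaving could therefore differ by arm and could depend on early progress. The documents do not say that this will happen, but nothing in them protects the comparison if it does. A week-4 scan that was never taken cannot be recovered later. With no population defined, exclusions could also be settled after the data are seen.

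**Working it through.** **1. The plan's own figure.** Inputs from Protocol 5.2: means 30 and 37, SD 10, so d = 7/10 = 0.7; power 0.80. Alpha is not stated; 0.05 two-sided is assumed.
- The base size of 19 reproduces as a one-sample (pre-post) t-test: n = 18.03, rounded up to 19.
- The allowance reproduces as 19 × 1.15 = 21.85, rounded up to 22.
- Under the usual inflation, 19/(1 − 0.15) = 22.35, rounded up to 23.
- Expected completers at 15% loss: 22 × 0.85 = 18.7. Three losses out of 22 is 13.6%; out of 19 it is 15.8%.
- On the plan's own calculation, power is 0.80 with 18 completers and 0.82 with 19. The gap is one patient per group and costs almost nothing.

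**2. Which outcomes have data to recover.**

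| Outcome | Visits (Protocol 5.6) | Week-2 value for a later leaver |
|---|---|---|
| fMRI, sEMG (primary) | weeks 0, 4 | none |
| FMA, Wolf, Brunnstrom, Barthel (secondary) | weeks 0, 2, 4 | yes, if the visit falls during treatment |

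**3. Size of a possible bias in FMA.** Assumptions not in the documents: mean 33.5 at week 2 (midway between 30 and 37); equal correlation r of 0.7 to 0.8 between any two visits; no true difference between arms; 15% of one arm leaves after week 2, more often those with a low week-2 gain; nobody leaves the other arm.
- SD of a gain = 10 × √(2(1 − r)): 7.75 at r = 0.7 and 6.32 at r = 0.8.
- Slope of week-4 gain on week-2 gain = (1 − r)/(2(1 − r)) = 0.5.
- Bias in completers' mean gain = 0.5 × SD of gain × upward shift in completers' mean week-2 gain (in SDs).
- If the lowest 15% all leave, the shift is φ(1.036)/0.85 = 0.2332/0.85 = 0.274. The bias is 0.5 × 7.75 × 0.274 = 1.06, or 0.5 × 6.32 × 0.274 = 0.87.
- If the odds of leaving rise e-fold per SD of lower gain, numerical integration gives a shift of 0.133. The bias is 0.51 or 0.42.

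Completers' mean gain is then 7.4 to 8.1 against a true 7.0, a false arm difference of about 0.4 to 1.1 points (6% to 15% of 7). Simulation with 2,000,000 patients agreed: 7.51 and 8.06 at r = 0.7; 7.41 and 7.87 at r = 0.8. An estimate that also used weeks 0 and 2 returned 6.99 to 7.01.

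**4. Other patterns of loss.** A separate model took the week-4 mean, let patients with low week-2 scores leave more often (logit slope 1.5 per SD), and set the week 2 to week 4 correlation at 0.5 to 0.9.

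| Loss by arm | Bias, FMA points |
|---|---|
| 15% v 15% | about 0 |
| 10% v 20% | 0.5 to 1.0 |
| 5% v 25% | 1.0 to 1.9 |

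**The case against.** The strongest reply is that the plan is silent rather than wrong. A reader might infer that it commits to analysing completers. It does not: the word appears nowhere, and nothing says that patients who stop go unassessed. A complete-case analysis is what the named tests do by default. That stands as a limit on the wording.

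A reader might also infer that week-2 data are thrown away generally. The primary outcomes have none. For the motor scores, the SAP as worded assigns t-tests to measurement data and repeated-measures ANOVA to counting data, and a separate t-test at week 2 would use a later leaver's week-2 score. What is lost is that score's contribution to the week-4 comparison. The time frame could also mean 2 and 4 weeks after treatment ends. On that reading a patient who leaves in week 3 has no interim score, and both the week-2 argument and the illustration in step 3 fall away.

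Unequal drop-off alone does not bias the contrast; leaving must also be related to outcome. The 0.4 to 1.1 points need selective loss in one arm and none in the other, whereas the protocol plans 15% in each group. The bias is also small against sampling error. With 22 against 18.7 patients, the standard error of a difference in gain is SD × √(1/22 + 1/18.7) = SD × 0.315, or 2.0 to 2.4 points, so the bias is about 0.2 to 0.45 of one standard error. The good performance of the estimate using weeks 0 and 2 follows from the set-up, in which leaving depends only on the week-2 gain. All of this stands.

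Finally, the 15% figure might be read as a material shortfall. The exact chance that a group of 22 keeps at least 19 at 15% loss is 58%, but with 23 it is still only 74%, and the power cost is trivial. It is a matter of wording.

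None of this supplies an analysis population, a way to use partial data, or a rule for follow-up.

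**Conclusion.** The point holds in limited form. Three spare patients per group are the only provision for drop-off, and the tests named would by default compare only patients with a week-4 value. If leaving depends on early progress and differs by arm, the motor-score contrast is biased. The size is about 0.4 to 1.1 FMA points under selective 15% loss from one arm only, up to about 1.9 at 5% against 25% in the separate model, and about 0 with the same rate and mechanism in both arms. These figures rest on assumed correlations and drop-off mechanisms and, in step 3, on a week-2 visit during treatment. They concern FMA, which is a secondary outcome but the one used to size the trial. For fMRI and sEMG there is no interim value to borrow, so the protection there is to obtain the week-4 measurement. The change is worth making because it is cheap and missed assessments cannot be recovered, not because a large bias has been shown.

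**What to change.** - **SAP:** state that all randomised patients are analysed in their allocated group. For the continuous motor scores, replace the default complete-case t-tests with a mixed model over weeks 0, 2 and 4 (the MIXED procedure in SPSS), with the week-4 arm contrast as the estimate.
- **Protocol 5.6:** state that patients who stop treatment are still assessed as scheduled, including week-4 fMRI and sEMG, unless they withdraw consent to assessment. Record the reason for stopping, by arm. State whether the 2-week and 4-week visits are counted from the start or the end of treatment.
- **Protocol 5.2 (minor):** restate the allowance as covering a loss of 3 of 22 (13.6%).

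The cost is some tracing of patients who stopped, a little more analysis work and a slightly lower stated allowance. No extra patients are needed. The mixed model does not cover Brunnstrom stage, which is ordinal, or the two-visit primary outcomes; for these the gain comes from continued assessment and analysis as allocated.
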